The Mediterranean diet (MD), a time-honored diet rich in plant-based foods and monounsaturated fat, such as olive oil, but low in saturated fats, dairy, and meat,⁸ has recently been considered a therapeutic dietary strategy for IBS. MD has been shown to have cardiovascular benefits in regard to both incidence and mortality,^{9,10} along with other benefits such as the decreased risk of overall mortality, cognitive disorders, and diabetes.¹¹ It is hypothesized that it could also be beneficial in reducing bowel symptoms due to its positive impact on the gut microbiota^{12,13} and microscopic inflammation,^{14,15} lower intake of saturated fat, and regulation of the gastro-colonic reflex.¹⁶ A population-based, cross-sectional study from Italy found the presence of IBS in the general population to be associated with low adherence to an MD.¹⁷ Furthermore, lower adherence to the MD has been associated with more severe abdominal pain and flatulence in patients with IBS.¹² However, it is not clear whether the lower adherence to MD causes more IBS symptoms or whether patients with IBS are more likely to avoid the MD due to worsening symptoms on this diet. A small, open-label study compared the efficacy of three dietary interventions, LFD, gluten-free diet, and MD, in IBS.¹⁸ Each patient followed the three diets for 4 weeks each. All three diets reduced symptom severity ($p<0.01$), abdominal bloating ($p<0.01$), and abdominal pain ($p<0.01$) when compared to baseline. Interestingly, 86% of patients preferred the Mediterranean diet ($p<0.01$). Limitations of the study include the small sample size, carry-over effects as well as lack of randomization, blinding, or assessment of adherence to the diet interventions. ***Despite this initial supportive evidence, no randomized controlled trial has investigated the efficacy of MD in IBS and MD is not routinely used in managing IBS symptoms.*** Therefore, there is a need to evaluate the efficacy of MD in managing IBS symptoms. ***Our overall objective is to compare the clinical efficacy of the MD with the LFD in patients with IBS in a single-center, parallel-group, randomized controlled trial.***

In this study, **we hypothesize that:**

1. LFD and MD groups will achieve a similar improvement in abdominal pain
2. Both groups will achieve similar improvements in bloating, overall IBS symptom severity, and adequate relief

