(P=0.002) but not with a specific FODMAP challenge. When we restricted the analysis to the first reintroduction period, galactan challenge was associated with the worsening of bloating (P=0.03).

Our group is also interested in understanding the mechanisms of how diet mediates IBS pathophysiology. Using rodent models, we have recently shown that a high fodmap diet causes gram-negative dysbiosis mediated mast cell activation which in turn leads to barrier dysfunction.³⁸ Furthermore, we have also validated that an LFD improves mast cell activation and barrier dysfunction in IBS-D patients.

In summary, our group, which includes expert gastroenterologists and specially trained research dietitians, is widely considered a leader in conducting clinical trials evaluating diet interventions in patients with FGIDs. We have successfully conducted various diet-based clinical trials and also utilized translational tools to understand the role of diet in the pathophysiology of IBS and biomarkers for response.

Research plan:

Patient population

Patients with IBS diagnosed using ROME IV criteria will be consecutively recruited from outpatient gastroenterology and primary care clinics at Michigan Medicine and via online advertisement.

Eligibility Criteria

Inclusion criteria

1. Patients with IBS-D (diarrhea-predominant IBS) or IBS-M (IBS with mixed subtype) diagnosed per Rome IV questionnaire and without any unexplained alarm features (rectal bleeding, weight loss, nocturnal symptoms, personal history of celiac disease, microscopic colitis, inflammatory bowel disease)
2. Aged 18-70 years at the time of screening
3. Weekly average of worst daily (in the past 24 hours) abdominal pain score of ≥ 3.0 on a 0-to-10-point scale
4. At least 80% compliance in daily questionnaire entries during the 7-day screening period

Exclusion criteria

[figure not shown]
1. Subjects adhering to any dietary IBS treatment such as the low-fat diet, LFD, or gluten-free diet, MD currently or within the past 6 months
2. Subjects with a known food allergy to eggs, seafood, peanuts, tree nuts or milk (subjects with lactose intolerance who are experiencing IBS symptoms while on a lactose-free diet will not be excluded from the study).
3. Subjects with a history of poorly controlled insulin-dependent or non-insulin-dependent diabetes
4. Subjects with a known history of organic GI disease (i.e., celiac disease, inflammatory bowel disease or microscopic colitis)

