5. Subjects with a history of an eating disorder requiring medical or behavioral treatment within the past 10 years.
6. Subjects with prior small bowel or colonic surgery (excluding appendectomy or cholecystectomy if over 6 months since these 2 procedures)
7. Oral antibiotic use in the past 3 months
8. Any planned significant changes in dietary or exercise regimen within 30 days prior to Screening or during the study.
9. Currently pregnant or breastfeeding.

Concomitant Medications

[figure not shown]
Subjects will be allowed to remain on their current IBS medications, provided a stable dose in the past 30 days and they fulfill entry criteria for symptom frequency and severity.

Study Design

This pilot study is designed to assess the comparative effectiveness of MD with LFD. Approximately 20 subjects will undergo a seven-day baseline screening period during which symptoms will be recorded. If a subject doesn't meet all eligibility criteria in the first seven days of the baseline screening period, the screening period can be extended up to 21 days. Subjects meeting all eligibility criteria will be randomized in a 1:1 ratio to receive either the MD or the LFD for a four-week period.

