- Abdominal Discomfort Intensity: The abdominal discomfort score is a single-question, 11-point numeric rating scale in which 0 represents no abdominal discomfort and 10 represents the worst possible abdominal discomfort. Once per day, subjects will report their worst daily (in the past 24 hours) abdominal discomfort.
- Abdominal Bloating: The abdominal bloating score is a single-question, 11-point numeric rating scale in which 0 represents no abdominal bloating and 10 represents the worst possible abdominal bloating. Once per day, subjects will report their worst daily (in the past 24 hours) abdominal bloating.
- Stool Frequency: Subjects will report the number of bowel movements over the previous 24 hours.
- Stool Form: Subjects will use the Bristol Stool Scale (BSS) to report the form of each bowel movement over the previous 24 hours.
- IBS Medication: Subjects will be asked whether they used an IBS medication over the previous 24 hours that is not typically taken daily (i.e., prn antispasmodic, loperamide or laxative).
- IBS-Adequate Relief: Subjects will provide a binary (yes or no) response to rate the adequacy of relief of global IBS symptoms at the start of the study and weekly thereafter.
- Quality of Life: Subjects will report quality of life measures specific to IBS using a validated 34-point questionnaire at the start and end of the study.
- IBS-SSS: Subjects will complete the IBS Symptom Severity Score questionaries at the start of the study and weekly thereafter
- Non-GI symptoms: non-GI symptoms often associated with IBS including fatigue, "brain fog", and quality of sleep will be assessed at the start and end of the study. Fatigue and brain fog will be scored using an 11-point numeric rating scale. Sleep quality will specifically be assessed with the PROMIS Sleep questionnaire.
- Anxiety: Anxiety will be assessed via GAD-7 score at the start and end of the study.

- Diet compliance: Patients will fill out the Mediterranean Diet Adherence Screener (MEDAS), described below, to assess their adherence to the Mediterranean diet at the start and end of the study. Given there are no high-quality, validated questionnaires to assess LFD adherence, a 3-day diet recall will be obtained at baseline and at the end of the study which will eventually be reviewed by a registered dietitian to confirm adherence to the LFD in the LFD group.

Chart A

	Day 0	Daily	Weekly	Day 28
Abdominal Pain		X		
Abdominal Discomfort		X		
Abdominal Bloating		X		

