- Abdominal pain intensity – Proportion of patients who would be weekly responders to abdominal pain for at least 2 of the 4 weeks. A weekly responder is defined as a decrease in the weekly average of worst abdominal pain in the past 24 hours score of at least 30% compared with baseline.

Secondary Endpoints

- Adequate relief - Proportion of patients who would be weekly responders to adequate relief symptom assessment for at least 2 of the 4 weeks. A weekly responder is defined as adequate relief in symptoms in at least 2 out of 4 weeks of the treatment period.
- IBS-SSS - Proportion of weekly responders for at least 2 of the 4 weeks. A weekly responder is defined as a decrease in the weekly IBS-SSS score of at least 50 points compared with baseline.
- Bloating - Proportion of patients who would be weekly responders to bloating for at least 2 of the 4 weeks. A weekly responder is defined as a decrease in the weekly average of worst bloating in the past 24 hours score of at least 30% compared with baseline.
- Stool consistency: Proportion of patients who would be weekly responders to stool consistency assessment for at least 2 of the 4 weeks. A stool consistency weekly responder will be defined as a 50% or greater reduction in the number of days per week with at least one abnormal stool (defined as BSS 1 or 2 or 6 or 7)

Exploratory endpoints:

- Mean changes in stool frequency, abdominal discomfort, IBS-QoL, anxiety, fatigue, brain fog, and sleep quality will be measured before and after the study.
- Stool and sera will be collected during the study and stored for future analyses. The stool will be stored for microbiome analysis, fermentation indices (short-chain and branched-chain fatty acid profiles), and bile acid profile and serum will be stored for analysis of the effect of diets on permeability using serological markers such as LPS, LBP, Zonulin, and inflammatory cytokines.
- Changes in breath hydrogen and methane pattern with the dietary interventions

Statistical Analysis

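### The adequate-relief responder rule ignores the Day 0 answer that the trial collects, so a patient already in relief who does not change counts as a responder

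*Combined protocol and SAP*

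**What the plan says.** Under Secondary Endpoints, the adequate-relief entry first asks for weekly response in at least two of four weeks. It then adds: "A weekly responder is defined as adequate relief in symptoms in at least 2 out of 4 weeks of the treatment period". Neither sentence refers to baseline.

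The other responder rules in the Endpoints section are all change rules. Pain and bloating each need a fall in the "score of at least 30% compared with baseline". IBS-SSS needs "a decrease in the weekly IBS-SSS score of at least 50 points compared with baseline". Stool consistency needs a reduction of at least half in days with abnormal stool.

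The Day 0 answer exists. Under Clinical Outcome Measures, subjects "rate the adequacy of relief of global IBS symptoms at the start of the study and weekly thereafter", and Chart A marks this item at Day 0, weekly and at Day 28. Neither the Endpoints section nor the Statistical Analysis section uses the Day 0 value. Proportions are compared by chi-square or Fisher's exact test, with no stratification.

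On entry, the symptom threshold in the inclusion criteria is a weekly average worst "abdominal pain score of ≥ 3.0 on a 0-to-10-point scale". Under Concomitant Medications, "Subjects will be allowed to remain on their current IBS medications, provided a stable dose in the past 30 days", as long as they still meet the symptom criteria. No criterion mentions adequate relief.

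Hypothesis 2 in Specific aims reads: "Both groups will achieve similar improvements in bloating, overall IBS symptom severity, and adequate relief".

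**The concern.** The hypothesis is about improvement, but the rule measures a state during treatment. Someone who answers 'yes' before eating any study food, and goes on answering 'yes', has not improved and is still counted as a diet responder. The trial asks the question that would identify this patient and then leaves the answer unused.

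What is at stake is how the responder rates are read. They could include relief that was present before the diets began. The difference between diets could also be smaller, on average, than among patients who had relief to gain. Because the predicted result is similarity, a reader of the report would need to know how much of it comes from patients who entered with relief.

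The circular wording is a separate defect and needs no assumption about Day 0. A weekly status is defined by a four-week count, and the preceding sentence then applies a two-of-four count again. No rule for a single week is written.

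**Working it through.** **Inputs from the protocol.** Total sample size 20 (Study Design; Statistical Analysis) and 1:1 allocation, so about 10 per arm. The 20 is given as a pilot number without alpha, power, effect or margin, and no expected rate is given for this endpoint. There is therefore no stated figure to reproduce.

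**Assumptions.** Let b be the share answering 'yes' at Day 0, taken as 5 to 30%. Let q be the responder rate among Day 0 'no' patients: 50% on the low-FODMAP diet (LFD), because Specific aims cites a success rate near 50%, though not for this endpoint; and 30% on the Mediterranean diet (MD), purely for illustration. Let s be the rate at which Day 0 'yes' patients meet the two-of-four rule. A patient who does not change has s = 1.

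**Step 1: expected rates.** Observed rate in an arm = (1 − b)q + bs. The inflation is b(s − q), so it is positive whenever s exceeds q. With the same s in both arms, the difference is (1 − b)(q_LFD − q_MD), whatever s is.

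For b = 20% and s = 1: LFD 0.8 × 50 + 20 = 60%; MD 0.8 × 30 + 20 = 44%; difference 16 points.

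| b | LFD | MD | Difference (points) | Chance of at least one Day 0 'yes' among 20 | Chance that the arms' Day 0 'yes' counts differ by 2 or more |
|---|---|---|---|---|---|
| 0 | 50% | 30% | 20 | – | – |
| 5% | 52.5% | 33.5% | 19 | 64% | 11% |
| 10% | 55% | 37% | 18 | 88% | 24% |
| 20% | 60% | 44% | 16 | 99% | 39% |
| 30% | 65% | 51% | 14 | 99.9% | 46% |

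The fifth column is 1 − (1 − b)^20. The last is P(|X − Y| ≥ 2) for two independent Binomial(10, b) counts.

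**Step 2: chance imbalance.** One patient is 10 points in an arm of 10. In 200,000 simulated trials with the rates above and s = 1, the observed gap was compared with the gap if the same patients had responded at their arm's q. At b of 10, 20 and 30% it moved in MD's favour in 36, 47 and 52% of trials, and in LFD's favour in 23, 26 and 26%.

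**Step 3: unequal retention.** If Day 0 'yes' patients keep relief in 90% of cases on LFD and 50% on MD (assumed), the difference is (1 − b) × 20 + b × 40. That is 22, 24 and 26 points at b of 10, 20 and 30%, so the gap widens.

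**Step 4: what each analysis recovers.** Among Day 0 'no' patients alone the difference is q_LFD − q_MD = 20 points. The cost is precision: the standard error, √[(0.5 × 0.5 + 0.3 × 0.7)/n], is 21 points at n = 10 per arm and 23, 24 and 26 points at n = 9, 8 and 7. A risk difference pooled over Day 0 strata is still (1 − b) × 20 points under equal retention. Stratifying deals with chance imbalance, not with dilution. Recoding Day 0 'yes' patients as non-responders also leaves (1 − b) × 20 points and removes only the inflation.

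**The case against.** The strongest case on the other side has four parts.

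First, a yes/no state has no percentage fall to require. Being in adequate relief on treatment, compared between randomised arms, is a coherent quantity. Day 0 status is balanced in expectation, so the rule creates no systematic difference where none exists. This stands, and it is why all randomised patients should stay in the main comparison. There is a further reason: Specific aims allows that patients may avoid MD because it worsens their symptoms. A Day 0 'yes' patient who loses relief is evidence on that question and should not be dropped.

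Second, Day 0 'yes' answers may be uncommon, since patients must reach the pain threshold while on any stable medication. This is fair, and it is why the table starts at 5%, where one point of 20 is lost.

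Third, a shift of 1 to 6 points is small against a standard error of 21. At 50% vs 30% with 10 per arm, the power of Fisher's exact test is 5.5% at b = 0 and 3 to 5% with dilution. No test in this pilot turns on the point, and the Limitations section says that the study is not definitive.

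Fourth, a reader might infer that the rates handed to the larger trial are wrong. The documents do not support that. If that trial kept the same entry criteria and rule, the all-randomised rate would be the right planning rate. The text also does not say that the margin will come from this endpoint; the primary endpoint is pain, which is referenced to baseline.

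None of this answers the two textual defects: the Day 0 answer is unused, and no rule for a single week is written.

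**Conclusion.** The point holds as a gap in the definition. Adequate relief is the only responder rule without a change from baseline, the Day 0 answer enters no endpoint or analysis, and nothing at entry excludes a Day 0 'yes'. An unchanged patient of that kind is scored as a responder, although the hypothesis is about improvement.

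The size is conditional. Both rates rise if such patients exist and meet the rule more often than Day 0 'no' patients do. The expected difference shrinks by the factor 1 − b if they also keep relief equally in both arms, which takes 1 to 6 points off an assumed 20 for b of 5 to 30%. The share b, the retention rates and the 50% and 30% response rates are all assumptions.

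A reader might infer that the rule makes the arms look alike and so favours the hypothesis. The documents do not support that as a general statement. It is an expectation under equal retention; unequal retention can widen the gap, and with about 10 per arm chance can move it either way. The consequence is modest: a secondary endpoint in a 20-patient pilot whose responder rates cannot be read as improvement without the Day 0 answer.

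**What to change.** 1. Define weekly response as a 'yes' to adequate relief in that week, and endpoint response as weekly response in at least two of the four treatment weeks. This removes the circularity.
2. Keep all randomised patients in the main comparison and stratify it by the Day 0 answer. With strata this small, show the counts in each stratum next to the pooled estimate. If one arm has no Day 0 'yes' patient, that stratum contains no comparison between diets.
3. Report the number of Day 0 'yes' patients by arm, and how many of them met the rule.
4. Give the result among Day 0 'no' patients as a supportive estimate of improvement, with its smaller denominator stated. The Day 0 answer precedes the diet, so this restriction keeps the randomised comparison valid.

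The cost is a reworded endpoint, a sentence in Statistical Analysis and one table. No new data are needed. The supportive estimate loses some precision (about 21 to 26 points of standard error in the worst case shown), which is a reason not to make it the main result.

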- Pregnancy test will be obtained in women of childbearing age if no reliable method of contraception is being utilized (e.g. IUD, OCP, implant)
- Subjects will be given two stool collection kits for at-home collection. One stool sample will be collected prior to beginning the treatment period. One stool sample will be collected on Day 28 (-1 day).
- Subjects will be instructed on the online questionnaires according to Chart A (described below) which will assess periodic symptoms and diet compliance to be completed for the duration of the study.

- Subjects will be instructed on the 3-day food diary to assess for nutritional content to be completed at the start and end of the study.
- A detailed dietary history will be obtained.

Screening Period

- Subjects will complete a 3-day food diary which will be analyzed for nutritional content.
- Subjects will complete a daily online questionnaire to assess symptoms
- For subjects who don't meet all eligibility criteria in the first seven days of the screening period, this period can be extended up to 21 days

Day 0 Visit (Visit #2)

- Patients who fulfill the inclusion and exclusion will be randomized to either the Mediterranean or low FODMAP cohorts (Diets A and B)
- Vitals will be obtained including height and weight at visit 2

Treatment Period

- Subjects will fill out a daily online questionnaire to assess symptoms and diet compliance according to Chart A throughout the treatment period.

Day 28 (End-of-treatment) Visit

- Subjects will complete a 3-day food diary which will be analyzed for nutritional content and compliance
- Adverse events and concomitant medications will be reviewed.
- Blood samples will be obtained.
- Post-treatment stool samples will be collected.
- Subjects will finish the last set of questionnaires

Clinical Outcome Measures

Online questionnaire entries will include the following measures, to be assessed on a frequency according to Chart A.

- Abdominal Pain Intensity: The abdominal pain score is a single-question, 11-point numeric rating scale in which 0 represents no abdominal pain and 10 represents the worst possible abdominal pain. Once per day, subjects will report their worst daily (in the past 24 hours) abdominal pain.

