All continuous variables will be tested for normality using the Shapiro-Wilk test. Normally distributed continuous data will be presented as mean (+/- SD) and will be compared pre-and post-dietary interventions using paired Student's t-test. Continuous data which are not normally distributed will be presented as median (range) and compared using Wilcoxon signed-rank test. Proportions will be expressed as percentages and compared using a chi-square test or fisher exact test as appropriate. As this is a pilot feasibility study, a sample size of 20 patients will allow us to get data on the outcomes and non-inferiority margin needed to power the larger Phase III multi-centered trial.

Potential difficulties

One of the potential difficulties might be the difficulty in patient recruitment for the study. Our group has successfully completed several pharmacological and diet-based RCTs in this patient population and has been able to recruit a much larger sample size for previous studies. However, to ensure we can recruit the required sample size, we will assign a study coordinator who will dedicate a significant proportion of her/his time to

recruiting patients from our functional and general GI clinics. Online and on-site advertisements will also be utilized to recruit patients from general gastroenterology and primary care clinics. We will further utilize a novel digital recruiting tool called “My GI Health” which will identify potential study subjects through social media platforms. We feel that this study will be attractive as we will be providing meals for the duration of the study. In addition, the lack of a placebo group will ensure that all participants will receive a potentially beneficial diet intervention. Other potential difficulties include patients being non-compliant with the diet. We are providing meals to all participants to minimize this and will obtain a daily food log, 3-day recall as well as MEDAS (Mediterranean Diet Adherence Scale) to ensure that our patients are compliant with their allocated diet arm.

Limitations

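### The stool-consistency responder counts abnormal-stool days without dividing by days reported, so if recorded entries are scored as written, a missed treatment diary day can favour response but never count against it (minor; secondary endpoint).

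*Combined protocol and SAP*

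**What the plan says.** Under Secondary Endpoints, a patient responds on stool consistency by being a weekly responder in two or more of the four weeks. The weekly criterion is a "50% or greater reduction in the number of days per week with at least one abnormal stool", where abnormal means Bristol type 1, 2, 6 or 7. The bullet does not mention days reported and does not name the comparator. The bloating responder in the same list is a "decrease in the weekly average of worst bloating in the past 24 hours score of at least 30% compared with baseline", and the primary pain responder has the same form.

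The data come from a diary. Under Clinical Outcome Measures, "Subjects will use the Bristol Stool Scale (BSS) to report the form of each bowel movement over the previous 24 hours", and Chart A schedules this daily. Under Treatment Period, "Subjects will fill out a daily online questionnaire to assess symptoms and diet compliance according to Chart A throughout the treatment period"; no minimum number of entries is attached.

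The only completeness requirement is an inclusion criterion: "At least 80% compliance in daily questionnaire entries during the 7-day screening period". If eligibility is not met in the first seven days, "the screening period can be extended up to 21 days" (Study Design; Screening Period agrees).

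For the responder endpoints, Statistical Analysis says only this: "Proportions will be expressed as percentages and compared using a chi-square test or fisher exact test as appropriate". It gives no rule for missing diary days or for weeks with few or no entries.

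**The concern.** A count of bad days falls for two reasons: the patient has fewer bad days, or reports fewer days. The endpoint as worded cannot tell these apart. A weekly average can, at least mechanically, because an unreported day leaves both the numerator and the denominator.

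Under the count, missed treatment diaries would raise the absolute stool response rate in any arm where they occur. The observed difference between diets could then shrink or widen even if completion were the same in both arms, because the inflation depends on where each arm's true rate sits relative to the threshold. Limitations says that the pilot will supply preliminary efficacy data for a larger trial, so an interpretable stool response rate is worth having.

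**Working it through.** The plan gives no figure for this endpoint, so there is nothing to reproduce. The check has three parts: direction, size with no true change, and size for a difference between diets.

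**1. Direction.** Let B be the baseline number of abnormal days and a the number recorded in a treatment week. The count rule is a ≤ 0.5 × B. With B = 7 the limit is 3.5. A patient with an abnormal stool every day who completes four diary days records 4, a non-response; with three completed days the record is 3, a response. A week with no entries records 0, which meets the limit for any B of 1 or more.

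Taking all baseline counts 1 to 7, all 128 seven-day patterns and each possible single missed day gives 7 × 128 × 7 = 6,272 cases:

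| Rule | To response | Away from response | Unchanged |
|---|---|---|---|
| Count | 581 | 0 | 5,691 |
| Proportion of reported days | 294 | 287 | 5,691 |

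A missed abnormal *screening* day works the other way: a true 6 recorded as 5 cuts the allowed whole-day count from 3 to 2. In a seven-day screening period the 80% criterion limits this to one day, since 6/7 = 85.7% passes and 5/7 = 71.4% fails. Treatment weeks have no such limit.

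**2. False response with no true change.** The documents give neither a completion rate nor an abnormal-day rate. Assumptions: independent days, days missed at random, a complete seven-day baseline, and a zero baseline scored as non-response.

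- Baseline count B ~ Bin(7, p)
- Completed days in a treatment week m ~ Bin(7, c)
- Abnormal days recorded a ~ Bin(m, p)
- Count rule: a ≤ 0.5B
- Proportion rule: m ≥ 4 and a/m ≤ 0.5 × B/7
- With w the weekly response probability given B, the patient responds with probability 1 − (1−w)⁴ − 4w(1−w)³, averaged over B

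| Abnormal days, p | Rule | c = 100% | 95% | 90% | 80% |
|---|---|---|---|---|---|
| 80% | Count | 0.4% | 1.2% | 3.2% | 12.8% |
| 80% | Proportion | 0.4% | 0.5% | 0.7% | 1.0% |
| 90% | Count | 0.0% | 0.1% | 0.4% | 4.6% |
| 60% | Count | 8.0% | 11.6% | 16.2% | 28.2% |
| 60% | Proportion | 8.0% | 7.8% | 7.9% | 7.9% |

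The 8% at p = 60% is chance variation, not missing data. At p = 80%, the excess per arm of 10 is 10 × (0.012 − 0.005) = 0.07 patients at 95% completion, 10 × (0.032 − 0.007) = 0.25 at 90%, and 10 × (0.128 − 0.010) = 1.2 at 80%. With a six-day baseline the count gives 0.2 / 1.6 / 6.8% at 100 / 90 / 80% completion, which shows the partial offset from a missed screening day.

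**3. Difference between diets.** Both arms start at 80% abnormal days and have equal completion; baseline is seven days. Entries are differences in response rate, in points.

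| On-diet abnormal days | Complete diaries | Count, 90% | Proportion, 90% | Count, 80% | Proportion, 80% |
|---|---|---|---|---|---|
| 30% vs 60% | 71.6 | 58.6 | 69.7 | 43.0 | 67.4 |
| 40% vs 60% | 54.5 | 47.0 | 52.2 | 35.8 | 49.0 |
| 50% vs 70% | 43.6 | 48.2 | 41.7 | 44.4 | 38.8 |
| 60% vs 80% | 20.6 | 33.5 | 21.0 | 41.5 | 20.6 |

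Count minus complete diaries is −13.0, −7.5, +4.6 and +12.9 at 90% completion, and −28.6, −18.7, +0.8 and +20.9 at 80%.

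**The case against.** The strongest reply is that the plan never says an unreported day is normal. What is documented is silence on missing diaries, and an analyst might well set sparse weeks aside or score them as failures. That stands: the direction follows only if the count is applied to recorded entries as worded. But no other convention is written down, and choosing one after seeing 20 patients' data would be a post hoc choice.

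The silence also covers the whole plan. Pain and bloating equally lack a minimum number of days and a rule for an empty week. What is specific to stool consistency is the count in place of an average.

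The proportion rule is not always closer to the complete-diary result. At 50% vs 70% and 80% completion, the count gives 44 points, the proportion 39 and complete diaries 44. With a six-day baseline at 60% vs 80%, the proportion gives 20.6 against 11.6 with complete treatment diaries, although the count is further off at 31.0.

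A reader might infer three stronger points that the documents do not support:

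- *A 21-day baseline total would be set against one treatment week.* The definition is in days per week, so a raw 21-day total is not its natural reading. The baseline window is simply unstated, for pain and bloating as well.
- *The comparison favours one diet.* Nothing suggests that diary completion will differ by arm.
- *The future trial's margin or size will rest on the stool rate.* The plan does not say so.

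**Conclusion.** The concern holds as a minor point. The stool responder is a count with no denominator, treatment diaries have no completeness rule, and under the count as worded a missed treatment day never works against response. The false-responder rate is negligible with near-complete diaries and reaches 12.8% only at 80% completion (80% abnormal days, seven-day baseline). The distortion of a between-diet difference is about 5 to 13 points at 90% completion and between 1 and 29 at 80%, with either sign. Completion rates, abnormal-day rates, independent days and random missingness are all assumptions.

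For scale, with 10 patients per arm the standard error of a difference near 50% is √(2 × 0.5 × 0.5 / 10) = 0.22, or 22 points. Sampling error in this pilot is therefore larger than the likely distortion unless diaries are poorly kept. The endpoint is secondary, and the primary pain endpoint does not have this particular defect.

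**What to change.** Define the weekly stool responder as a reduction of 50% or more from baseline in the proportion of completed diary days with at least one abnormal stool. In addition:

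- State the baseline window, for example the last seven screening days before randomisation. The stool bullet does not name baseline, and screening may be extended.
- Set a minimum number of completed days per week, for example 4. Count weeks below it, including empty weeks, as non-response, and keep all randomised patients in the denominator.
- Report diary completion by arm.

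This needs wording only; Chart A already collects stool form daily. The cost is that sparse weeks become non-response: the chance of fewer than 4 completed days out of 7 is 0.3% at 90% completion and 3.3% at 80%. Detection of true improvement falls slightly. With a seven-day baseline, a patient going from 80% to 30% abnormal days is classed as a responder 92.5 / 91.4 / 88.9% of the time at 100 / 90 / 80% completion. The 4-day minimum is a judgement: with 3 or 5 days, the false-responder rate at 80% completion is 1.1% or 0.6% instead of 1.0%.
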